2.3.9 Withdrawal of Informed Consent

Any data collected in the clinical database after a subject withdraws informed consent from all further participation in the trial, will not be included in the analysis. The date on which a patient withdraws full consent is recorded in the eCRF.

Additional data for which there is a separate informed consent, e.g. PK, biomarker etc., collected in the clinical database without having obtained that consent will not be included in the analysis. These data will be excluded by the presence of the appropriate protocol deviation criterion.

2.3.10 Subgroup analyses

Select summaries of efficacy will also be presented by treatment and will be based on PD-L1 expression with predefined thresholds (Section 3.7).

2.4 Sample size and power considerations

Please refer to [CPDR001X2101 Amendment 8 Section 10.8].

2.5 Interim analyses

No formal interim analyses are planned. However, the dose-escalation design foresees that decisions based on the current data are taken before the EOS. More precisely, after each cohort in the Phase I dose-escalation part, the next dose is to be chosen depending on the observed data.

3 Statistical methods used in reporting

3.1 Patient disposition, background and demographic characteristics

Unless noted otherwise, summaries and listings described in this section will be based on the FAS.

3.1.1 Patient disposition

The following patient disposition information will be listed and summarized by treatment group for all patients in FAS at time of reporting.

- Enrolled patients who remained on treatment or discontinued treatment at the time of cutoff
- EOT: Primary reasons for EOT based on EOT eCRF
- EOS: Study evaluation completion after EOT:
 - Patients who are either no longer being followed up for study evaluation or who continued to be followed for study evaluation based on EOT eCRF

A listing of EOT details will be produced. Patients enrolled but not treated will be listed along with the reason for discontinuing from the study. Screen failures will not be included in any of the summary tables, but will be reported in separate listings.

3.1.2 Demographic characteristics

All demographic and baseline disease characteristics data will be summarized and listed. Categorical data, e.g. gender, age groups: 18 - <65 years and ≥ 65 years, race, ethnicity, weight categories: <55, 55 - <75, and >=75 kg, ECOG performance status, will be summarized by frequency counts and percentages; the number and percentage of patients with missing data will be provided. Continuous data, e.g. age, weight, height, will be summarized by descriptive statistics (N, mean, median, standard deviation, minimum and maximum).

3.1.3 Medical History

Relevant and current medical history will be summarized and listed. The summaries were to be presented by primary system organ class and preferred term and coded using the latest Medical Dictionary for Regulatory Activities (MedDRA) terminology available at the time of reporting.

3.1.4 Diagnosis and extent of cancer

Diagnosis and extent of cancer (disease history) will be summarized for the following variables: diagnosis of disease, details of tumor histology/cytology, histologic grade, stage at initial diagnosis, time (in months) since initial diagnosis, time (in months) from initial diagnosis to first recurrence/relapse, time (in months) since most recent recurrence/relapse to treatment start, types of lesions (target and non-target lesions) at baseline, current extent of disease (metastatic sites).

Due to the imputation method for partially missing dates, the time intervals indicated above could be computed as negative. In such situation, they must be handled as missing dates.

Patient listings with disease history details will be provided.

3.1.5 Prior anti-neoplastic therapy

All prior anti-neoplastic medication, radiotherapy and surgery will be listed.

The number (%) of patients who received any prior anti-neoplastic medication, radiotherapy or surgery will be summarized.

The summary of prior anti-neoplastic medications will include the total number of regimens (note: there can be more than one medication per regimen), therapy type at last treatment, setting at last treatment, time (in days) from last treatment to progression, best response at last treatment (defined to be the best response during the last treatment regimens recorded). Prior

SAP final CSR 24-Jul-2020 (11:48)

antineoplastic medications will also be summarized by Anatomical Therapeutic Chemical class, and preferred term.

The summary of prior anti-neoplastic radiotherapy will include the radiotherapy locations, (including all locations recorded for each patient), setting at last radiotherapy, and best response at last radiotherapy.

The summary of prior anti-neoplastic surgery will include the time (in months) between the last surgery (non-biopsy procedure) to start of study treatment, procedure at last surgery and residual disease at last surgery.

3.1.6 **Protocol deviations**

The FAS will be used for the protocol deviation summary tables and listing. The number (%) of patients with any CSR-reportable protocol deviation will be tabulated by the deviation category (selection criteria not met, study treatment deviation, not discontinued after meeting withdrawal criteria, use of prohibited concomitant medicine and other deviation). The full list of CSR-reportable protocol deviations is documented in the Study Specification Document (SSD). All protocol deviations will be listed by treatment.

3.2 Treatments (study treatment, concomitant therapies and compliance)

Study treatment is PDR001.

3.2.1 Study treatment exposure

The safety set is used for all summary tables and listings for drug exposure.

3.2.1.1 Date of first administration of study treatment

The date of first administration of study treatment is defined as the first date when a nonzero dose of study treatment (PDR001) was administered and recorded on the PDR001 dosage administration record (DAR) electronic case report form (eCRF). This date is also referred to as start date of study treatment.

3.2.1.1.1 Date imputation of the first administration of study treatment

Subjects with missing start dates are generally considered missing for all study treatment related calculations described in Section 3.2.1.4 and no imputation will be made. If the date of first administration is missing, then the date of last administration should not be imputed.

However, if the dosing information at C1D1 is entered on the PK DAR page, the date on this page will be used to impute the first administration date. Before imputing the date, it will be checked that the date is not after the second administration or after the end date of the first record.

Date of last administration of study treatment 3.2.1.2

The date of last administration of study treatment is defined as the last date when a nonzero dose of study treatment (PDR001) was administered and recorded on the DAR eCRF. This date is also referred to as last date of study treatment.

3.2.1.2.1 Data imputation for the last administration

The following rule should be used for the imputation of date of last administration for study treatment:

Scenario 1: If the date of last administration is completely missing and there is no EOT eCRF page, the subject is considered as on-going:

The subject should be treated as on-going and the cut-off date should be used as the last dosing date.

Scenario 2: If the date of last administration is completely or partially missing and the EOT eCRF page is available (prior to any death date or withdrawal of consent date, if available):

Case 1: The date of last administration is completely missing, and the EOT visit date is complete, then this latter date should be used.

Case 2: Only Year(yyyy) of the dose end date is available and yyyy < the year of EOT date:

Use Dec31yyyy

Case 3: Only Year(yyyy) of the dose end date is available and yyyy = the year of EOT date:

Use EOT date

Case 4: Both Year(yyyy) and Month (mm) are available for the date of last administration, and yyyy = the year of EOT date and mm < the month of EOT visit:

Use last day of the Month (mm).

After imputation, compare the imputed date with the start date of that specific record, if the imputed date is < start date of that record

Use the start date of that record.

3.2.1.3 Last date of exposure to study treatment

PDR001every 2 weeks (Q2W) administration:

Last date of exposure = min(last date of administration of PDR001 + 13 days, death date, cut-off date).

PDR001 every 3 weeks (Q3W) administration:

Last date of exposure = min(last date of administration of PDR001 + 20 days, death date, cut-off date).

PDR001every 4 weeks (Q4W) administration:

Last date of exposure = min(last date of administration of PDR001 + 27 days, death date, cut-off date).

3.2.1.4 Duration of study treatment exposure

The following algorithms will be used to calculate the duration of study treatment exposure (in days and in cycles) for patients taking at least 1 dose of the study treatment:

Duration of exposure (days) = last date of exposure to study treatment - date of first administration of the study treatment + 1

SAP final CSR

Duration of exposure (cycles) = calculate the duration of exposure as stated above and then consider the patients exposed to the study treatment for one cycle if he/she received at least 70% of the planned dose of PDR001 within the cycle.

For patients who did not take any study treatment, the duration of exposure is defined as zero.

The exposure duration may include periods of temporary interruption. If a patient is still on treatment at the time of data cut-off, the end date of treatment will be replaced by the data cutoff date and the above respective algorithm will be used.

3.2.1.5 Dose delay/interruption

Any dose change/delay flagged in the DAR eCRF page, satisfying the following criteria:

- a reason other than "as per protocol"
- a zero actual dose
- occurs between the first and last non-zero doses
- follows a nonzero actual dose.

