#### 6.1.1 Dosing regimen

**Table 6-1 Dose and treatment schedule**

Study treatments	Pharmaceutical form and route of administration	Dose	Frequency and/or Regimen
PDR001	Powder for solution for infusion	1 mg/kg (starting dose)	Every 2 weeks (or alternative regimens, e.g. Q3W, Q4W)

PDR001 will be administered via i.v. infusion over 30 minutes (up to 2 hour, if clinically indicated) once every 2 weeks. The next dose may be delayed by up to 7 days to recover from previous AEs (see [Section 6.3.2](#)) before receiving the next dose. If the next dose cannot be administered within the above mentioned 7-day delay, then the dose should be skipped. Dosing will resume at the next scheduled dose and assessment schedule will be shifted accordingly. Dose modifications should follow [Section 6.3.1](#) and [Section 6.3.2](#).

If a significant number of patients require dose delays due to PDR001-related toxicities, or if the PK data support it, the dosing regimen for the study may be changed to once every 28 days. This will be discussed in a dose escalation teleconference at the time of the proposed change and documented in the meeting minutes accordingly (see [Section 6.2.3](#)). Alternative dosing regimens may also be considered based on clinical toxicity and preliminary PK/PD and efficacy findings.

Once the RP2D dose and schedule are determined, patients from the dose escalation who have completed 4 cycles of treatment may be offered the option of switching to the RP2D (dose and schedule). If this change leads to an increase in the dose, then the patient must fulfill the criteria outlined in [Section 6.2.3.4](#) for inpatient dose escalation.

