Hematology Neutropenia (ANC) Grade 3 or Grade 4 Febrile neutropenia Grade 3 or Grade 4 Thrombocytopenia Grade 3 Grade 4 Anemia Grade 3 or Grade 4 Lymphopenia Any grade	Hold study treatment. Upon resolution to $\leq$ Grade 2 or baseline within $\leq$ 7 days, resume study treatment without dose modification, after discussion with the Novartis Medical Monitor. Hold study treatment. Upon resolution of fever and improvement of neutropenia to $\leq$ Grade 2 or baseline, resume study treatment without dose modification, after discussion with the Novartis Medical Monitor. Hold study treatment. Upon resolution to $\leq$ Grade 2 or baseline, resume study treatment without dose modification. For Grade 3 associated with major bleeding, discontinue study treatment. Discontinue study treatment. Hold study treatment. Upon resolution to $\leq$ Grade 2 or baseline within 7 days, resume study treatment without dose modification. Treatment-related lymphopenia does not require study treatment hold or discontinuation.
Other laboratory adverse events, not specified elsewhere in table and not included in the consensus guidelines Grade 3	Hold study treatment. Upon resolution to $\leq$ Grade 1, resume study treatment without dose modification.

TOXICITY	FOLLOW-UP EVALUATION AND TREATMENT RECOMMENDATIONS
Grade 4	Isolated Grade 4 electrolyte abnormalities not associated with clinical sequelae and corrected after appropriate management within 72 hours of their onset do not require discontinuation. In the case of Grade 4 electrolyte imbalances associated with clinical sequelae, or not resolved to $\leq$ Grade 1 within 72 hours despite appropriate management, discontinue study treatment.
Other non-laboratory adverse events, not specified elsewhere in table and not included in the consensus guidelines	
Grade 2	Consider study treatment hold, at Investigator discretion. Upon resolution to $\leq$ Grade 1, resume study treatment without dose modification.
Grade 3	Hold study treatment. Upon resolution to $\leq$ Grade 1, resuming study treatment must be discussed with the Novartis Medical Monitor.
Grade 4	Discontinue study treatment.

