3.2.2 Study treatment

The duration of exposure, actual cumulative dose, dose intensity (DI) and relative dose intensity (RDI) will be summarized by treatment group for the safety set.

To assess tolerability, dose delay and dose reduction for the study treatment will be summarized by treatment group. By-patient listings will be provided.

Summary of duration of exposure of study treatment will include categorical summaries (based on clinically meaningful time intervals like < 4 weeks, 4-8 weeks, 8-12 weeks, >=12 weeks etc.) and continuous summaries (i.e. mean, standard deviation etc) using appropriate units of time.

The actual cumulative dose of the study treatment, DI, RDI and RDI categories to measure compliance will be summarized with descriptive statistics by treatment. The predefined

categories for RDI are $< 0.5, \ge 0.5 - < 0.75, \ge 0.75 - < 0.9, \ge 0.9 - < 1.1$ and ≥ 1.1 . The number and proportion of patients within each category will be presented by treatment group.

The number (%) of patients who have dose reductions or interruptions, and the reasons, will be summarized by treatment. Patient level listings of all doses administered on treatment along with dose change reasons will be produced.

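### SAP 3.2.1.5 counts a dose delay or interruption only when the dose is zero, so an infusion given late is not counted as written, although SAP 3.2.2 says delays will be summarised

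*SAP*

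**What the plan says.** Protocol 6.1.1 gives two outcomes for a patient who is not ready for the next infusion. Either the infusion is late but given: "The next dose may be delayed by up to 7 days to recover from previous AEs". Or it is not given at all: "If the next dose cannot be administered within the above mentioned 7-day delay, then the dose should be skipped".

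SAP 3.2.1.5 covers delay and interruption with a single definition. It starts from "Any dose change/delay flagged in the DAR eCRF page, satisfying the following criteria" and then lists conditions that must all hold: the recorded reason is not that the protocol called for the change; there is "a zero actual dose"; the record "occurs between the first and last non-zero doses"; and it "follows a nonzero actual dose".

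SAP 3.2.2 then commits to an output: "To assess tolerability, dose delay and dose reduction for the study treatment will be summarized by treatment group". The same section also plans counts of patients with reductions or interruptions, with reasons.

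Table 3-1 of the protocol names three tolerability components: interruptions, reductions and dose intensity. Protocol 10.5.3.6 asks for counts and reasons for interruptions and reductions.

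On relative dose intensity (RDI) the two documents differ. Protocol 10.3 divides dose intensity by planned dose over planned duration. SAP 3.2.1.9 divides both actual and planned cumulative dose by the same duration of exposure.

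**The concern.** The SAP promises a summary of delays, but its only definition of a delay requires that nothing was infused. The late-but-given infusion, which the protocol treats as distinct from a skip, is then left out of the count. RDI, which SAP 3.2.2 uses to measure compliance, does not make up for this, because as defined it does not respond to lateness. A reader of the exposure tables could see no delays and an RDI of 1 in a group where infusions were repeatedly postponed. Protocol 6.1.1 itself treats a high number of toxicity-related delays as a possible reason to change the regimen, so the count carries information.

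**Working it through.** The documents give no figure of their own on this point, so the check applies the written rules to example courses.

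**Step 1: the criteria.** Take an infusion given 7 days late at full dose and recorded only as that infusion. Its actual dose is not zero, so it fails 3.2.1.5. It is not a reduction (3.2.1.6 needs a lower dose) or an increment (3.2.1.7 needs a higher one). No other rule in the SAP classifies it.

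**Step 2: the entry convention.** If the site also enters a zero-dose record for the missed day, that record is zero, follows a given dose and precedes the late one, so it counts. The documents contain no completion rule for the dosage administration record (DAR). SAP 2.1.3.4 handles an extra rest week before the next cycle by lengthening the cycle and mentions no missed dose. That suggests a late infusion need not generate a zero record, but it does not settle the matter.

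**Step 3: dose intensity and RDI.** Inputs are 400 mg Q4W and 300 mg Q3W (the protocol's phase II regimens), and last exposure at last dose + 27 or + 20 days (SAP 3.2.1.3). Assumptions are six full infusions, no death or data cut-off in the last interval, and a planned duration of six intervals. With D the dose, τ the interval, n = 6 and L the total days late:

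- Duration = (n − 1)τ + L + (τ − 1) + 1 = nτ + L
- Dose intensity (DI) = nD / (nτ + L)
- SAP planned dose intensity (PDI) = nD / (nτ + L), so SAP RDI = 1 whatever L is
- Protocol RDI = DI / (D/τ) = nτ / (nτ + L)

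| Course | Days | DI (mg/day) | Count, 3.2.1.5 | SAP RDI | Protocol RDI |
|---|---|---|---|---|---|
| Q4W, no delay | 168 | 2400/168 = 14.29 | 0 | 1.000 | 1.000 |
| Q4W, one 7-day delay | 175 | 2400/175 = 13.71 | 0 | 1.000 | 168/175 = 0.960 |
| Q4W, five 7-day delays | 203 | 2400/203 = 11.82 | 0 | 1.000 | 168/203 = 0.828 |
| Q3W, no delay | 126 | 1800/126 = 14.29 | 0 | 1.000 | 1.000 |
| Q3W, one 7-day delay | 133 | 1800/133 = 13.53 | 0 | 1.000 | 126/133 = 0.947 |
| Q3W, five 7-day delays | 161 | 1800/161 = 11.18 | 0 | 1.000 | 126/161 = 0.783 |

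For comparison, one skipped dose within a Q4W course of six given infusions lasts 7 × 28 = 196 days, has DI 2400/196 = 12.24 and counts 1. Five delays lower DI further (11.82) and count 0.

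If delays were entered as zero-dose records, the counts for one and five delays would be 1 and 5. In the RDI categories of SAP 3.2.2, the five-delay courses fall in 0.9 to under 1.1 on the SAP formula but in 0.75 to under 0.9 on the protocol formula. One delay does not change the category.

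**The case against.** The best case against is that delay is visible elsewhere and that the protocol never asked for a delay count. Table 3-1 and Protocol 10.5.3.6 name interruptions, not delays, so counting zero-dose events does not depart from the protocol endpoint. DI is part of that endpoint and falls with each delay. The SAP also tabulates AEs that caused dosing to be interrupted or adjusted, and lists all doses with the reasons for changes. And the eCRF is not in the documents, so nobody can say that a late infusion can never produce a qualifying record.

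Most of this stands, and it limits the point. A reader might infer that delays are missing from the tolerability endpoint. They are not, because DI reflects them. A reader might also infer that every late infusion escapes the count; that depends on the entry convention. What the objection does not remove is the conflict inside the SAP: 3.2.2 promises a delay summary and 3.2.1.5 cannot produce one as written. DI gives no number of patients and no reasons, and the AE table and listings do not summarise late infusions.

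**Conclusion.** The point holds as a conflict between SAP 3.2.1.5 and 3.2.2, with a related departure of the SAP's RDI from Protocol 10.3. On the rules as written, late infusions add 0 to the delay/interruption count and leave the SAP's RDI at 1.000, where the protocol formula gives 0.828 (Q4W) or 0.783 (Q3W) for five 7-day delays in six infusions. These courses are illustrations. The documents do not say how often delays occurred, and the zero counts assume that a hold is not entered as a zero-dose record. The effect is confined to descriptive tolerability output; nothing here touches response rate, DLT evaluation or dose selection.

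Three further inferences are tempting but not supported:

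- **Table 6-4 holds.** Wording such as "or baseline within 7 days, resume study treatment without dose modification" limits the time for a toxicity to recover, not how late the next infusion is. An event that resolves between infusions may delay nothing, so the table does not show that such holds go uncounted.
- **Skips that end in discontinuation.** They fall outside the definition, but those patients appear under the end-of-treatment reason and, where an AE was the cause, in the AE tables. Counting them again as interruptions is a preference.
- **A bias between regimens.** The 7-day allowance stands in a paragraph written for dosing every 2 weeks, groups are summarised separately, and no formal comparison of tolerability is planned.

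**What to change.** In SAP 3.2.1.5, replace the single definition with two:

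- **Dose delay:** a non-zero infusion flagged as delayed on the DAR, with a reason other than that the protocol called for it. Days late are computed from the infusion dates and the planned interval.
- **Dose interruption (skip):** the existing zero-dose criteria, unchanged.

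Report the number and percentage of patients, and the reasons, for each by treatment group. Using the DAR flag avoids choosing a lateness tolerance, which would be awkward beside the ±7-day visit window in Protocol 7.1. State how a hold is entered on the DAR, so that one event is not counted both as a delay and as a skip. Either reconcile the SAP's PDI with the planned duration in Protocol 10.3, or say plainly that RDI as defined does not reflect delay.

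The cost is a wording change and some programming from flags, reasons and dates that the DAR is described as holding. The reported number of delays will look less favourable.

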3.2.1.6 Dose reduction

Any dose change/delay flagged in the DAR eCRF page, satisfying the following criteria:

- a reason other than "as per protocol"
- a nonzero actual dose below the immediate previous nonzero actual dose,
- a non-zero actual dose below the treatment assigned as per safety set.

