### **6.2.3.4 Intra-patient dose escalation**

For patients enrolled in the Phase I part of the study, intra-patient dose escalation is not permitted at any time within the first 4 cycles of treatment. After cycle 4 is completed, individual patients may be considered for treatment at a dose of PDR001 higher than the dose to which they were initially assigned and/or a different dosing regimen. In order for a patient to be treated at a higher dose of PDR001, he or she must have tolerated the lower dose for at least 4 cycles of therapy (i.e. he or she must not have experienced any PDR001-related toxicity CTCAE grade  $\geq 2$  at the lower dose originally assigned). Moreover, the new, higher dose with which the patient is to be treated must be a dose that has completed evaluation and has not exceeded the maximum tolerated dose (MTD). There is no limit to the number of times a patient may have his or her dose of PDR001 increased. For any further increase after the initial intra-patient dose escalation, the following rules apply: the patient must have experienced no CTCAE grade  $\geq 2$ , PDR001-related toxicity over at least two cycles of therapy at the lower dose, and the higher dose being considered must have been fully evaluated and shown not to exceed the MTD. Consultation and agreement with Novartis must occur prior to any intra-patient dose escalation occurring. These changes must be recorded on the Dosage Administration Record eCRF. Data from the first cycle of treatment at the new dose level will not be formally included in the statistical model describing the relationship between dose and occurrence of DLT. However, these data will be incorporated into the clinical assessment of safety during dose escalation teleconferences.

For patients enrolled in the phase II part of the study, intra-patient dose escalation or change in dosing regimen is not permitted.

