2.1.2 Other definitions

Cohort: a group of newly enrolled patients treated at a specific dose and regimen (i.e. treatment group) at the same time in the Phase I dose-escalation part. Cohorts are not expanded, new cohorts are enrolled.

Treatment group: patients coming from different cohorts but being treated at the same dose level/schedule. Treatment groups are determined by the initially planned PDR001 dose level on Cycle 1 Day 1. A treatment group can include several cohorts of patients who received the same dose level/schedule but were recruited at a different point during the study.

Dose-limiting toxicity: an AE or abnormal laboratory value of CTCAE grade > 3 assessed as unrelated to disease, disease progression, inter-current illness or concomitant medications, which occurs within the first cycle of treatment with PDR001 during the Phase I dose escalation part of the study, with the exceptions described in [CPDR001X2101 Amendment 8 Table 6-3].

Maximum tolerate dose (MTD): the highest safe dose of PDR001 given as a single agent for a given schedule that causes DLTs in no more than 33% of patients during the first cycle of treatment (28 days).

End of treatment (EOT): at any time, patients may voluntarily withdraw from the study or be removed from it at the discretion of the Investigator. The primary reasons for EOT are AEs; disease progression; protocol violation /deviation; patient withdrew consent; lost to follow up; administrative problems; death.

SAP final CSR 24-Jul-2020 (11:48)

Patients who discontinue study treatment for any reason (except death) were to be scheduled for an EOT visit within 14 days at which time all of the assessments listed on [CPDR001X2101 Amendment 8 Table 7-1] for EOT visit were to be performed.

End of study (EOS): the end of the study will be when 80% of the patients per disease group in the Phase II part have completed the follow-up for disease progression or discontinued the study for any reason, and all patients have completed treatment and the 150 day safety followup period, or if the study is terminated early. The definition is for the planned time point to end this study.

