2.3.2 Safety set

The Safety Set (SS) includes all patients from the FAS who have received at least one dose of PDR001 and had at least one valid post-baseline safety assessment. The statement that a patient had no AEs (on the AE eCRF) constitutes a valid safety assessment. Patients will be classified according to treatment received, where treatment received is defined as:

- The treatment assigned if it was received at least once, or
- The first treatment received when starting therapy with study treatment if the assigned treatment was never received.

The safety set will be used for the safety summary of the study.

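### In Phase I patients escalated within patient, the SAP's dose-reduction rule leaves out of the tabulation any cut that lands at or above the starting dose

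*SAP*

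**What the plan says.** SAP 3.2.1.6 opens its definition of a dose reduction with "Any dose change/delay flagged in the DAR eCRF page, satisfying the following criteria" and lists three conditions:

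1. the recorded reason is not a per-protocol change;
2. the dose is "a nonzero actual dose below the immediate previous nonzero actual dose";
3. it is "a non-zero actual dose below the treatment assigned as per safety set".

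The reference in the third condition comes from SAP 2.3.2, which classifies a patient by "The treatment assigned if it was received at least once" and otherwise by the first treatment received. SAP 2.1.2 adds: "Treatment groups are determined by the initially planned PDR001 dose level on Cycle 1 Day 1".

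Protocol 6.2.3.4 permits intra-patient escalation in Phase I once four cycles are complete, and states: "There is no limit to the number of times a patient may have his or her dose of PDR001 increased". It does not permit escalation in Phase II. Protocol 6.3.1 allows dose or schedule adjustments for patients who do not tolerate treatment.

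Dose reductions are a named tolerability endpoint (Protocol Table 3-1, SAP Table 1-1). Protocol 10.5.3.6 calls for the number of reductions to be summarised, with reasons, and does not restrict them to doses below the assigned level. SAP 3.2.2 delivers this as the number and percentage of patients by treatment.

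**The concern.** The third condition works for a patient who stays at the assigned dose: any real reduction then falls below it. It stops working once the patient has been escalated, because the reference stays at the starting level while the dose being tolerated, or not tolerated, is higher. A cut for toxicity from the higher dose meets the third condition only if it goes below the starting level.

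The rule can therefore only under-count, and only among patients who had a higher dose and then came down from it. SAP 3.2.1.7 already identifies intra-patient escalation from the planned dose, so the plan foresees the situation, but the reduction rule was not adapted to it.

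**Working it through.** No sample size or power is involved. The check applies the stated rule to dose paths.

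**Are the conditions joint?** The list contains no *or*. The parallel lists for interruption (SAP 3.2.1.5) and increment (3.2.1.7) make sense only if every item must hold. Read as alternatives, the reduction list would count any change with a non-protocol reason, including an increase. The joint reading is the one to use.

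**Step-downs after an escalation.** The levels are those of Protocol Table 6-2: 0.3, 1, 3 and 10 mg/kg, with 0.3 used only as a landing dose. The reason is taken to be an AE, so condition 1 holds. Condition 2 holds for every step-down. Condition 3 is: new dose < assigned dose.

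| Assigned | Change (mg/kg) | Condition 3 | Counted? |
|---|---|---|---|
| 1 | 3 → 1 | 1 < 1, false | no |
| 1 | 3 → 0.3 | 0.3 < 1, true | yes |
| 1 | 10 → 3 | 3 < 1, false | no |
| 1 | 10 → 1 | 1 < 1, false | no |
| 1 | 10 → 0.3 | 0.3 < 1, true | yes |
| 3 | 10 → 3 | 3 < 3, false | no |
| 3 | 10 → 1 | 1 < 3, true | yes |
| 3 | 10 → 0.3 | 0.3 < 3, true | yes |

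Four of eight are missed: every cut that lands at or above the starting level. An intermediate dose behaves the same way: assigned 3, 10 → 5 fails because 5 < 3 is false.

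**Patients never escalated.** Assigned 1, 1 → 0.3; assigned 3, 3 → 1; and assigned 10, 10 → 3 all meet the three conditions. The rule treats them correctly.

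**Does relative dose intensity show the cut?** Under SAP 3.2.1.8 the planned cumulative dose is the sum of prescribed doses. Under 3.2.1.9, RDI = (actual dose / duration) / (planned dose / duration), so the duration cancels. Assume 8 infusions at 1, 4 at 10 and 4 at 3 mg/kg, all fully infused, in a 70 kg patient:

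- actual = 70 × (8×1 + 4×10 + 4×3) = 70 × 60 = 4200 mg
- planned = the same prescriptions = 4200 mg
- RDI = 4200 / 4200 = 1.00

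Body weight cancels too; 50 kg and 90 kg also give 1.00. When the prescription is lowered, the denominator falls with it.

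**The case against.** The strongest reply is that little is lost. The change is entered on the dosage administration record. SAP 3.2.2 lists every dose by patient with the reason for change. SAP 3.5.2.2 tabulates AEs leading to dose interruption or adjustment. A reader might infer that the event goes unrecorded; the documents do not support that. Only the derived reduction count misses it.

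A reader might also infer that Phase I tolerability was made to look better than it was. No such case is shown, and the protocol makes one fairly unlikely. Escalation requires at least four cycles without PDR001-related toxicity of grade 2 or higher, no DLT had occurred in the 58 patients treated, and Table 6-4 mostly holds treatment, resumes it without dose modification, or discontinues it. Adjustments remain permitted, so the case is possible, but its frequency is unknown.

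Four of eight is not a rate either: it weights dose pairs equally and says nothing about how many patients or events fall in each. Nor is an effect on reductions after a switch to the RP2D demonstrated. The RP2D is a flat 400 mg Q4W, and the step-downs checked are in mg/kg.

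Finally, the tables group patients by starting dose. Counting a 10 → 3 cut would place it in the 1 mg/kg row, where it could be read as intolerance of 1 mg/kg. This stands, and the fix has to deal with it. It does not justify leaving the event out of a summary that the protocol describes without such a limit.

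**Conclusion.** The definition is wrong as written for a case the protocol foresees. In escalated Phase I patients, a non-protocol cut to a dose at or above the starting level is not tabulated as a reduction. The error always under-counts, and RDI does not reveal it.

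Its size cannot be computed, because the documents do not say how many of the 58 Phase I patients were escalated and later reduced; it is probably small. The primary endpoints and all of Phase II are untouched. The conclusion rests on reading the three conditions as joint and the assigned treatment as the Cycle 1 Day 1 level, and the text supports both. It concerns a derived variable only; no view is taken on any dose or clinical rule.

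**What to change.** Replace the third condition in SAP 3.2.1.6 with: *the nonzero dose given is lower than the planned dose in force immediately before the change, including any protocol-permitted escalation or switch to the RP2D*. Keep the other two conditions.

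The words *immediately before the change* are needed. If the reference were the planned dose at the reduced infusion itself, a prescription lowered to 3 mg/kg would give planned 3 and actual 3, and the cut would be missed again. With the proposed wording, assigned 1, 10 → 3 is compared as 3 < 10 and counted. A return to plan after an accidental overdose is still excluded, which simply deleting the third condition would not achieve. Never-escalated patients whose planned dose has not changed are classified as now.

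Also show, in the table or a footnote, the dose level in force when each reduction occurred, so that it is not attributed to the starting-dose group.

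The cost is one line of SAP text, slightly more programming and possibly a slightly higher reported count. SAP 3.2.1.7 already uses the planned dose.
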